1.1 Background and Significance

1.2 Objective

1.3 References

## 1.1 Background and Significance

---

Glaucoma causes progressive damage and death of retinal ganglion cells (RGCs) resulting in blindness. The prevalence of the disease will rise to a projected 3 million Americans by 2020. A central yet unresolved issue in glaucoma is determining, in individual subjects, the onset of the disease. This is defined as the stage at which retinal ganglion cells (RGC) have lost their autoregulatory ability in response to a chronically stressful biomechanical, vascular or molecular environment, and become increasingly dysfunctional over time until they die and are eliminated from the neuronal pool. Were the duration of the stage of RGC dysfunction preceding death known, then it would represent the ideal time window for initiating therapeutic strategies to prevent cell death and visual loss.

Recent studies pioneered by our group in human and mouse models of glaucoma showed that RGC dysfunction, measured with the Pattern Electro-retinogram (PERG), can be restored after intraocular pressure (IOP) lowering. In addition, RGC dysfunction may be induced in susceptible eyes of mice and human in association with temporary IOP elevation during head-down body tilt (HDT). Further, our group has demonstrated that patients with substantially lowered PERG amplitude in Standard Seated Position (SSP) undergo more rapid Retinal Nerve Fiber Layer (RNFL) thinning than do patients with normal PERG.

If RGC function is modifiable in response to IOP modulation, then this represents both a rationale for treatment and a target to change the natural history of the disease.

## 1.2 Objective

---

The principal objective of this study is to prospectively follow glaucoma suspects (GS) with depressed PERG amplitude, either in SSP or upon HDT, who have been randomized either to observation or to receive either pressure lowering medicines and compare them with respect to longitudinal RNFL thinning from baseline. Further objectives include confirmation of previously published and unpublished findings suggesting that: pressure lowering medicines improve PERG amplitude in eyes with depressed SSP PERG amplitude; substantially depressed SSP PERG amplitude is a risk factor for more rapid RNFL thinning in eyes not receiving pressure lowering medications; and that delayed PERG phase upon HDT in combination with hemodynamic measurements is predictive of RNFL thinning in eyes not receiving pressure lowering medications.

### **2.1 Inclusion Criteria**

---

All of the criteria listed below must be present in the study eye in order for the patient to be eligible for enrollment in the study.

- a. Age 18 to 85 years, inclusive
- b. Refractive errors within -5 to +3 diopters
- c. Best corrected visual acuity (BCVA) better than or equal to 20/30 (Snellen)
- d. Normal standard automated perimetry (SAP) according to the Ocular Hypertension Treatment Study (OHTS) criteria (reliability < 15% on all indices, normality > 5% on all global indices in two consecutive sessions 6 months apart)
- e. Glaucoma Suspect Status defined as one or more of the following:
  - Glaucomatous optic disc appearance (vertical cup-to-disc ratio [C/D]  $\geq 0.5$ )
  - Cup disc ratio asymmetry  $\geq 0.2$
  - Localized thinning of the disc
  - Presence or history of splinter disc hemorrhage
  - Moderately increased IOP ( $>21$  to  $<28$  mm Hg).
  - Family history of vision loss for glaucoma

## 2.2 Exclusion Criteria

---

If any of the following exclusion criteria are present in the study eye, the patient may not be entered into the study.

- a. Age-related macular degeneration
- b. Diabetes
- c. Parkinson's disease
- d. Multiple sclerosis
- e. Unwilling or unable to give consent, unwilling to accept randomization, or unable to return for scheduled protocol visits.
- f. Pregnant or nursing women.
- g. Currently using prescribed pressure lowering medicines and unwilling to be withdrawn from them.
- h. An OHTS risk score high enough in the judgment of the ophthalmologist or optometrist managing the patient to recommend pressure lowering medicine to the patient and not randomization.
- i. An OCT abnormal enough in a pattern consistent with glaucoma.

## 2.3 Stratification of patients

---

*Definition:* Abnormal SSP PERG amplitude is defined as  $\leq 60\%$  of age specific normal. The logarithm of age specific normal PERG amplitude is obtained from the regression equation published by Ventura et al (IOVS 2006; 47:3904-11)

$$\log \text{expected normal amplitude} = 0.612 - 0.374 \times \log (\text{age in years}).$$

*Definition:* Susceptible to HDT is defined in the following way.

- a. The effect of HDT on PERG Phase (*EPP*) is calculated as:

$$EPP = 3.433 * (\text{Phase}_{HDT} - \text{Phase}_{SSP}) - 308.465 \times \text{Phase}_{HDT} \div \text{Phase}_{SSP}$$

where each phase variable is expressed as percent of age specific normal. The age specific normal phase is obtained from the regression equation (Ventura et al) =  $1.99 - 0.0027 \times \text{age}$ .

- b. The effect of HDT on hemodynamic variables (EHV) is calculated from measurements of Systolic Brachial Pressure (SBrP) and Ocular Perfusion Pressure (OPP).

$$EHV = 24.815 \times (\text{SBrP}_{HDT} \div \text{SBrP}_{SSP}) + \text{OPP}_{SSP}$$

c. These two variables are substituted into the logistic equation

$$\text{Probability} = \exp(\text{EPP} + \text{EHV}) \div (1 + \exp(\text{EPP} + \text{EHV}))$$

A probability so obtained which is  $> 0.3$  is considered susceptible.

Patients eligible for inclusion in the study will be stratified into one of three groups based on the results of PERG testing at baseline.

1. Patients with abnormal baseline SSP PERG in one or both eyes (average of two measurements in different sessions) will be included in stratum 1, abnormal PERG (GS-A). Patients in this stratum will be randomized to observation or pressure lowering medicines.
2. Patients with neither eye abnormal by SSP PERG but demonstrated susceptible to HDT in one or both eyes – average of two measurements - will be included in stratum 2, HDT susceptible (GS-S). Patients in this stratum will be randomized to observation or pressure lowering medicines.
3. Patients with both eyes neither abnormal nor susceptible will be included in stratum 3 (GS-N). Patients in this stratum will be observed and not offered randomization.

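### The Section 2.3 head-down-tilt susceptibility equation cannot be right as printed: its phase effect changes sign at a seated phase of 89.85% of normal, and its 0.3 cut-off is out of reach.

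*Combined protocol and SAP*

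**What the plan says.** Section 2.3 builds the score in three steps.

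- **Phase part:** EPP = 3.433 × (PhaseHDT − PhaseSSP) − 308.465 × PhaseHDT/PhaseSSP, "where each phase variable is expressed as percent of age specific normal". The age norm is 1.99 − 0.0027 × age.
- **Hemodynamic part:** EHV = 24.815 × (SBrP tilted/SBrP seated) + seated OPP. OPP enters with a coefficient of 1.
- **Decision:** the sum EPP + EHV goes through a logistic function with no intercept. "A probability so obtained which is $> 0.3$ is considered susceptible".

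The result fixes the stratum. GS-S takes "Patients with neither eye abnormal by SSP PERG but demonstrated susceptible to HDT in one or both eyes", and these patients are randomized. Patients with neither abnormality go to GS-N and are only observed.

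Section 1.2 gives the expected direction. One objective is to confirm that "delayed PERG phase upon HDT in combination with hemodynamic measurements is predictive of RNFL thinning in eyes not receiving pressure lowering medications". Nowhere do the documents say whether a delay is a lower or a higher phase value. Section 2.5 plans a separate test in each randomized stratum and quotes about 60% thinning in untreated GS-S patients and about 15% in GS-N.

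**The concern.** The phase difference and the phase ratio carry nearly the same information, yet they enter with opposite signs. At a seated phase of 100% the ratio term cancels about 90% of the difference term (3.085 of 3.433 per point). The sign of the remainder depends on the seated phase, whereas Section 1.2 describes one direction.

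The level is also suspect. A coefficient of −308 on a ratio near 1 has no intercept to offset it.

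The score is the gate to randomization for everyone whose seated PERG amplitude is normal. If it cannot be computed sensibly, one of the two randomized comparisons in Section 2.5 has no defined population. The objective of confirming that tilt-induced delay predicts thinning would also rest on a score that partly points the other way.

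**Working it through.** The documents give no worked score, so there is no stated figure to reproduce.

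**Inputs from Section 2.3:** coefficients 3.433, −308.465, 24.815 and 1 (on OPP); phases in percent of age normal; cut-off 0.3.

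**Assumed, because the documents give no values:** phases 50–150% of normal, OPP 30–100 mm Hg, SBrP ratio 1.0–1.2.

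**1. Direction.** The change in EPP per point of tilted phase is 3.433 − 308.465/PhaseSSP. It is zero at 308.465/3.433 = 89.85.

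| Seated phase, % of normal | Slope per point | Effect of a 10-point fall on tilt |
|---|---|---|
| 70 | −0.974 | +9.74 |
| 80 | −0.423 | +4.23 |
| 89.85 | 0 | 0 |
| 95 | +0.186 | −1.86 |
| 100 | +0.348 | −3.48 |
| 120 | +0.863 | −8.63 |

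If a delay is a fall in phase, it lowers the score above 89.85%. If a delay is a rise, it lowers the score below 89.85%. Neither convention agrees with Section 1.2 across the range.

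**2. Level.** A probability above 0.3 needs EPP + EHV > ln(0.3/0.7) = −0.847.

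- With unchanged phase the difference is 0 and the ratio is 1, so EPP = −308.465 at every seated phase.
- With SBrP ratio 1 and OPP 50, the score is −308.465 + 24.815 + 50 = −233.65.
- With unchanged phase and ratio 1, OPP would have to exceed −0.847 + 308.465 − 24.815 = 282.8 mm Hg.
- At seated phase 100% and OPP 50, the tilted phase would have to rise by 232.80/0.3483 = 668 points. At 80% it would have to fall by 232.80/0.4228 = 551 points, which is impossible.
- Over phases 50–150% the largest EPP is −282.2. The most favourable hemodynamics assumed (ratio 1.2, OPP 100) give −282.2 + 29.8 + 100 = −152.4. No grid point passes 0.3.

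**3. Phases as fractions.** This departs from the printed unit. It removes the reversal from any realistic range (the slope at a seated phase of 1 is 3.433 − 308.465 = −305.0). However, EPP at unchanged phase is still −308.465, and a 5% fall moves the score by −0.17 + 15.42 = 15.25. The unit alone does not repair the equation.

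**4. What a level-only repair would do (illustration).** Suppose an intercept of +232.80 had been left out, so that an unchanged eye with ratio 1 and OPP 50 sits at 0.30. The phase slopes stay as they are.

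| Seated phase, % of normal | Probability after a 10-point fall | Probability after a 10-point rise |
|---|---|---|
| 80 | 0.967 | 0.006 |
| 100 | 0.013 | 0.933 |

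The same tilt response would then be susceptible in one eye and not in the other.

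**The case against.** The strongest objection concerns consequence. A reader might infer from the sign reversal that patients are being sent to the wrong stratum. The printed equation does not support that. An eye more than 150 logit units below the cut-off stays there whichever way its phase moves, so every patient without an abnormal seated PERG goes to GS-N. This objection stands in full. The reversal matters only once the level is repaired.

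A second objection is that a difference plus a ratio lets the effect of tilt depend on seated phase, which a fitted model may do on purpose. Section 1.2 also speaks of phase in combination with hemodynamic measurements and does not promise the same direction at every seated phase. This is possible, and without the model output it cannot be excluded. But the plan does not say so, and a reversal within 11 points of the normal value needs a stated reason.

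Third, the equation may simply be incomplete or mistranscribed. That is the likeliest explanation, because Section 2.5 quotes a thinning rate for GS-S from preliminary data, which suggests that a working rule existed. It supports checking the equation before any remodelling.

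Fourth, GS-A is defined by amplitude and is unaffected. Any GS-S comparison would still be randomized within its stratum, so a faulty score would change the target population and event rate and would not bias the treatment contrast. This also stands.

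**Conclusion.** The equation cannot serve as printed. Two results hold:

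- The phase effect reverses at a seated phase of 89.85% of age normal. This is algebra on the printed coefficients and unit, and it conflicts with the single direction in Section 1.2 under either meaning of delay.
- The score lies about 233 logit units below the cut-off for an unchanged eye at an assumed OPP of 50 mm Hg, and at least about 151 units below it over the whole assumed range (−152.4 against −0.847). GS-S would be empty, although Section 2.5 plans a test there.

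The second result rests on the assumed ranges, but its margin is so wide that moderate changes to them would not alter it.

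A reader might want to state what share of eyes is scored backwards. The documents give no mean or spread of seated phase, do not define delay, and offer no true stratum to judge against. The affected eyes lie above 89.85% under one convention and below it under the other, so no misclassification percentage is supportable.

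Because the rule governs entry to a randomized stratum, it must be settled before patients are stratified.

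**What to change.** Before any patient is stratified:

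1. Check the Section 2.3 equation against the fitted model output: intercept, both phase coefficients and their signs, phase unit, and OPP coefficient. Print the corrected equation.
2. State which numerical direction of phase is a delay.
3. Add a worked example showing that a delay raises the probability and that 0.3 can be reached with realistic values.
4. Re-run the classification of anyone already stratified.

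This costs a check of existing output and a paragraph in Section 2.3.

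Only if the check confirms the printed phase coefficients should the sponsor go further, and either justify the reversal in the text or refit with a single phase-shift term. A refit needs the individual preliminary data, whose availability and size the documents do not state. The 0.3 cut-off and the thinning rates for GS-S and GS-N (60% and 15%) would then have to be re-read from the new model, and the sample size in Section 2.5 looked at again. If the check finds a misprint, no refit is needed.

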## 2.4 Randomization

---

After a patient has been placed in their study stratum, the Biostatistics Center will issue them a study ID number. The Biostatistics Center will provide patients in strata 1 or 2 (GS-A, GS-S) with their randomized treatment assignment to observation or pressure lowering medicines. Randomization will be performed within each stratum in a permuted variable block fashion to ensure approximate balance of treatment assignments within strata.

## 2.5 Analysis and Sample Size Calculations

---

Percentages of patients with RNFL thinning after four years of follow up will be compared between the observation and pressure lowering medicine groups. RNFL thinning is defined as a decrease in average RNFL of  $4.0\mu\text{m}$  (Budenz, (Invest Ophthalmol Vis Sci. 2010;51:5724 –5730)).

Preliminary data suggest that about 40% of untreated patients in stratum 1 (GS-A) will have incident RNFL thinning, while about 60% of untreated patients in

stratum 2 (GS-S) will have incident RNFL thinning. These data also suggest that about 15% of patients in stratum 3 (GS-N) will have incident RNFL thinning.

If pressure lowering medicines reduce the risk of RNFL thinning in patients in strata 1 and 2 to 15%, then about 32 patients in each randomized treatment group would provide 80% power. 42 patients in each randomized treatment group would provide 90% power.

If pressure lowering medicines do not reduce the risk of thinning to 15% but only to half the risk in the untreated patients, then 66 patients in each group would provide 80% power.

These calculations assume separate independent un-corrected significance tests in each stratum. If pressure lowering medicines had similar effects in each stratum, a pooled analysis would have substantially more power.

---

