## **7.3 Randomization Procedure**

---

Randomization takes place at the time the patient is enrolled in the study. After patient eligibility is confirmed and a patient identification number is provided, the Statistical Coordinating Center assigns treatment by saying, “Treatment” or “No Treatment”. The Clinical Center then repeats the assigned treatment. The treatment/no treatment date is the study entry date, and the dates for all follow-up visits are computed from this date.

The randomization schedule is constructed using a computer pseudo-random number generator. The allocation ratio is equal between the two treatment groups. The randomization is blocked by clinic and study stratum using a scheme with small variable blocks. This procedure ensures that there is an equal number of patients in each treatment group even early in the trial, and that the CC is not able to predict the next treatment assignment.

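### Section 2.5 specifies no covariate adjustment: the named predictors serve only as stratum cut-points and baseline RNFL is unused, which costs some precision but not validity.

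*Combined protocol and SAP*

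**What the plan says.** The main comparison is in section 2.5: "Percentages of patients with RNFL thinning after four years of follow up will be compared between the observation and pressure lowering medicine groups". The endpoint is binary: "RNFL thinning is defined as a decrease in average RNFL of" 4.0 µm. No test, model, covariate or effect measure is named there, and no adjusted analysis appears elsewhere.

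Section 1.2 sets out to confirm that "substantially depressed SSP PERG amplitude is a risk factor for more rapid RNFL thinning in eyes not receiving pressure lowering medications". It makes a similar claim for head-down-tilt (HDT) PERG phase combined with hemodynamic measurements, again in untreated eyes. Section 2.3 turns both into categories: seated (SSP) amplitude at or below 60% of age normal defines GS-A, and an HDT probability above 0.3 defines GS-S. Randomization is within stratum (2.4), and the sample size in 2.5 assumes a separate test in each stratum, with a pooled analysis mentioned as an alternative.

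Section 7.3 adds clinic: "The randomization is blocked by clinic and study stratum using a scheme with small variable blocks". Sections 2.4 and 5.3 name stratum only.

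OCT, IOP and PERG are all scheduled at baseline (Table 1 in 7.4), and the data sheets in 8.3 record PERG amplitude and phase, IOP and birth date.

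**The concern.** A cut-point balances a category, not the value within it. Two GS-A patients can lie at quite different distances below the 60% limit, and nothing in the analysis uses that difference. Baseline average RNFL is also unused, although the outcome is a dichotomised change from it: a baseline reading that is high by measurement error makes a 4.0 µm fall more likely.

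If such values predict thinning within a stratum, an analysis without them has less power than the same data could give. A chance difference between arms would also stay in the estimate. At 32 to 66 per group such differences are not rare. Treatment is unmasked (2.6), so covariates chosen after the results are seen would carry little weight. The list has to be fixed beforehand.

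**Working it through.** **1. The plan's own figures.** Inputs from 2.5: "Preliminary data suggest that about 40% of untreated patients in stratum 1 (GS-A) will have incident RNFL thinning"; the corresponding GS-S figure is 60%; treated risk is 15% or half the untreated risk. Assumed: two-sided 0.05 (not stated) and an untreated rate of (40% + 60%)/2 = 50% (inferred).

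n = [1.96·√(2p̄q̄) + z_β·√(p₁q₁ + p₂q₂)]² / (p₁ − p₂)², then the continuity correction n_cc = (n/4)·[1 + √(1 + 4/(n·|p₁ − p₂|))]².

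For 50% v 15% at 80% power, p̄ = 0.325:
- n = (1.96·0.662 + 0.842·0.614)² / 0.1225 = 26.9
- n_cc = (26.9/4)·(1 + √1.425)² = 32.4, or 33 rounded up; the plan says about 32.

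The same method gives 42 for 90% power and 66 for 50% v 25%, both as stated. These are unadjusted two-proportion calculations.

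**2. Power with and without adjustment.** The within-stratum strength is assumed. There were 10,000 simulated trials per setting, with one standard-normal baseline covariate acting equally in both arms. A pooled chi-square was compared with a logistic likelihood-ratio test adjusted for the covariate.

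| Setting | Log-odds 0.5 per SD (OR 1.65) | 1.0 (OR 2.72) | 1.5 (OR 4.48) |
|---|---|---|---|
| 40% v 15%, n=32 | 64% to 67% | 64% to 71% | 63% to 77% |
| 40% v 20%, n=66 | 72% to 75% | 71% to 79% | 72% to 85% |
| 50% v 15%, n=32 | 88% to 89% | 88% to 92% | 87% to 95% |
| 50% v 25%, n=66 | 86% to 87% | 86% to 91% | 86% to 94% |

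A covariate of no value neither helped nor hurt (50% v 15%, n=32: 87.4% v 87.5%).

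On the scale OR 1.5, 2 and 3 per SD, the gains for the two 40% settings are about 1-2, 2-5 and 7-10 points. At 60% v 15%, n=32, power is already 97-98% and rises to 98-99%. If the predictor acts only in untreated patients, which is how 1.2 words it, the gain is about 0-2.5 points. Simulation error is about 1 point.

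**3. Chance imbalance.** The standardised arm difference of a baseline covariate has SD √(2/n). At n=32 this is √(2/32) = 0.25. So P(>0.25 SD) = P(|Z|>1) = 32%, and P(>0.5 SD) = P(|Z|>2) = 4.6%. At n=66 the SD is 0.174, and the probabilities are 15% and 0.4%. With untreated risk 40-50%, a 0.5 SD imbalance moves the observed risk difference by about 6, 10 or 13 points at log-odds 0.5, 1.0 and 1.5. The planned differences at n=32 run from 40 − 15 = 25 to 60 − 15 = 45 points.

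**4. How many covariates the data can carry.** At 40% v 15% with 32 per group, expected events are 32·0.40 + 32·0.15 = 17.6. With three covariates and both arms at 15%, likelihood-ratio type I error rose to about 6-8%, against 5.1-5.3% unadjusted. With both arms at 40% or 50%, n=32 and one covariate, it was 5.4-6.0%, against 5.5-6.3% unadjusted.

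**5. The HDT score as a covariate.** The 2.3 formula was evaluated as printed, with assumed inputs: seated phase 100% of normal, HDT phase 95% to 150%, equal blood pressures, OPP 50.
- At 95%: EPP = 3.433·(−5) − 308.465·0.95 = −310.2.
- At 150%: EPP = 3.433·50 − 308.465·1.5 = −291.0.
- EHV = 24.815 + 50 = 74.8.

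The sum runs from about −235 to −216, so the probability is essentially 0 throughout. The score cannot serve as a covariate until that formula is reconciled.

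**The case against.** The strongest reply is that the plan does use its predictors. They define the strata, randomization is within stratum, and the tests are sized by stratum, so the main split is already balanced and analysed. That stands, and a reader who infers that the plan ignores its predictors goes too far. Nor does 2.5 rule out adjustment. It is silent on method, and a standardised difference in percentages would fit its wording.

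The size of the gain is also open to doubt. Section 1.2 treats the associations as findings to be confirmed, in untreated eyes only, and no document gives a gradient below the 60% cut. Baseline RNFL, IOP and age are not named as predictors of thinning. All this stands. It limits the claim to a modest and uncertain gain, with 7-10 points needing an odds ratio near 3 in both arms.

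Two practical points also stand. Strata are assigned to patients on the basis of one or both eyes, whereas amplitude and RNFL belong to an eye, so a covariate list must say which eye is meant. And the documents do not show that several clinics are randomizing.

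The reply does not remove the point. No adjustment is specified, the values are already collected, and a useless covariate cost essentially nothing in the simulation.

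**Conclusion.** The point holds as a modest improvement worth making. Section 2.5 specifies no adjustment, and within-stratum PERG amplitude and baseline average RNFL go unused. At the GS-A rate the expected gain is about 1-2, 2-5 or 7-10 points of power for odds ratios of 1.5, 2 or 3 per SD acting in both arms. It is 0-2.5 points if the predictor acts only in untreated patients, and small at 60% v 15%. These figures rest on an assumed strength of association, a two-sided 0.05 level and a single prognostic covariate.

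Two stronger readings are not supported. One is that the unadjusted comparison is invalid or biased: randomization makes it valid, and chance imbalance affects precision and the single-trial estimate. The other is that adjustment would rescue GS-A. The plan's 32, 42 and 66 reproduce only with a 50% untreated rate. At 40% v 15%, 32 per group gives about 61% power by the normal approximation (53% by Fisher's exact test), and adjustment reached at most 77% over the simulated range. That shortfall is a separate matter.

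**What to change.** Amend 2.5 as follows.

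- **Estimate:** make the primary result a covariate-standardised difference in percentages with thinning, from a logistic model, so the question stays the same.
- **Covariates:** fix at most two. Use baseline average RNFL in both strata, plus continuous baseline SSP PERG amplitude (percent of age normal) in GS-A. Take them from the same eye, or eye summary, that defines the outcome. Leave the HDT score out of GS-S until the 2.3 formula is reconciled.
- **Design factors:** include stratum in any pooled analysis. Include clinic only if randomization is actually blocked by clinic, and reconcile 7.3 with 2.4 and 5.3.
- **Test:** at 32 per group use a small-sample method, such as a permutation test that respects the blocking or penalised likelihood, because events are few.
- **Sensitivity analysis:** report the raw percentages and their unadjusted comparison.

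The cost is a paragraph of analysis-plan text. No patient, visit or measurement is added. The downside is some dependence on a model and, without the small-sample method, a slightly raised type I error when events are few.

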### **3.8 Optical Coherence Tomography**

---

Quantitative image analysis of the retinal nerve fiber layer (RNFL) and Ganglion Cell (GCA) is performed with Zeiss-Cirrus according to the protocol of (Mwanza et al, Ophthalmology 2012, 119:1151-1158). Cirrus HD-OCT is used to acquire 1 macular (Macular Cube 200×200 protocol) and 1 optic disc (Optic Disc Cube 200×200 protocol) scan in each qualifying eye after pupil dilation with tropicamide 1% and phenylephrine 2.5%. Only good-quality scans, defined as scans with signal strength  $\geq 6$ , without RNFL discontinuity or misalignment, involuntary saccade or blinking artifacts, and absence of algorithm segmentation failure on careful visual inspection, are used for analysis. Peripapillary RNFL thickness analysis includes the average, superior, and inferior quadrant thicknesses. Parameters from the ONH analysis include the rim area, cup-to-disc area ratio, and vertical cup-to-disc diameter ratio, which were measured automatically by the Cirrus internal ONH analysis algorithm. The GCA algorithm detects and measures the thickness of the macular GCIPL within a 14.13-mm^2 elliptical

annulus area centered on the fovea. The following GCIPL thickness measurements are analyzed: average, minimum, and sectoral (superior, superonasal, inferonasal, inferior, inferotemporal, and superotemporal).

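### Section 2.5 quotes power for randomised patients, but the sizes are best reproduced with every patient having a usable year-4 OCT; losses could lower that power, by an amount that depends on test and stratum

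*Combined protocol and SAP*

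**What the plan says.** Section 2.5 compares the percentage of patients with RNFL thinning (a fall of 4.0 µm in average thickness) after four years. For a treated risk of 15% it states that "about 32 patients in each randomized treatment group would provide 80% power" and that "42 patients in each randomized treatment group would provide 90% power". If treatment only halves the risk, "then 66 patients in each group would provide 80% power". The first two sizes are explicitly counts of randomised patients.

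The untreated risks differ by stratum: "Preliminary data suggest that about 40% of untreated patients in stratum 1 (GS-A) will have incident RNFL thinning", against "about 60% of untreated patients in" stratum 2 (GS-S). The section adds: "These calculations assume separate independent un-corrected significance tests in each stratum". It gives no numerical alpha, names no test and sets no recruitment target.

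Section 3.8 restricts the data: "Only good-quality scans, defined as scans with signal strength" of at least 6, and free of artefact and segmentation failure, are analysed. Section 7.4 schedules OCT at each annual visit and again at a repeat of the year-4 visit. Nowhere do the documents give an expected proportion lost or unevaluable, or say how a patient without a usable year-4 OCT is counted.

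**The concern.** The endpoint exists only for a patient who is still in the study at year 4 and has acceptable scans at both ends. If the sizes were calculated for complete data but are read as numbers to randomise, the trial analyses fewer patients than the calculation assumed. The groups are small and each stratum is to be tested separately, so a few missing outcomes per group can matter. The risk is one of interpretation: a null result in a stratum would be read against 80% or 90% power that the randomised numbers may not have provided.

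**Working it through.** **Inputs.** From 2.5: untreated risk 40% (GS-A) and 60% (GS-S); treated risk 15%, or half the untreated risk; sizes 32, 42 and 66 per group. From 7.3: equal allocation. Assumed because not stated: two-sided alpha 0.05; loss *d* of 10, 20 or 30%, equal in both groups; patients without the endpoint leave the analysis.

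**1. Reproducing the plan's sizes.** With p̄ the mean of the two risks:

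n = [1.960·√(2p̄(1−p̄)) + z·√(p₁(1−p₁) + p₂(1−p₂))]² ÷ (p₁−p₂)²

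Continuity-corrected: n_c = (n/4)·[1 + √(1 + 4/(n·|p₁−p₂|))]²

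For 50% v 15% at 80% power (z = 0.842, p̄ = 0.325): n = (1.298 + 0.517)² ÷ 0.1225 = 26.9, and n_c = 32.4.

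| Risks | Power | Uncorrected n | Corrected n | Plan |
|---|---|---|---|---|
| 50% v 15% | 80% | 27 | 33 | 32 |
| 50% v 15% | 90% | 36 | 42 | 42 |
| 50% v 25% | 80% | 58 | 66 | 66 |
| 40% v 15% | 80% / 90% | 49 / 65 | 57 / 73 | – |
| 60% v 15% | 80% / 90% | 17 / 23 | 22 / 27 | – |

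The corrected column at 50% matches the plan with no loss. Neither stated stratum rate does. The 50% is the midpoint of 40% and 60% and is not in the text.

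**2. Effect of loss at the reproducing 50% risk.** Evaluable patients are n(1−d), rounded: 32 becomes 29/26/22, 42 becomes 38/34/29 and 66 becomes 59/53/46 at 10/20/30% loss. Power is the sum of the two binomial probabilities over all tables with p ≤ 0.05.

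| n randomised (stated power) | Test | 0% | 10% | 20% | 30% |
|---|---|---|---|---|---|
| 32 (80%) | Fisher | 81.5 | 75.7 | 70.6 | 60.8 |
| | chi-square | 87.5 | 83.1 | 80.9 | 71.6 |
| 42 (90%) | Fisher | 91.6 | 88.6 | 83.7 | 75.7 |
| | chi-square | 94.6 | 92.5 | 89.9 | 83.1 |
| 66 (80%) | Fisher | 81.3 | 75.4 | 71.3 | 62.5 |
| | chi-square | 85.6 | 80.9 | 77.7 | 69.9 |

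**3. Effect at the plan's own stratum rates** (Fisher, same enumeration).

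| n randomised | Stratum and risks | 0% | 10% | 20% | 30% |
|---|---|---|---|---|---|
| 32 | GS-A, 40% v 15% | 53.1 | 46.7 | 40.8 | 35.0 |
| 32 | GS-S, 60% v 15% | 95.9 | 92.9 | 90.7 | 82.7 |
| 42 | GS-A, 40% v 15% | 67.2 | 61.9 | 54.5 | 46.7 |
| 42 | GS-S, 60% v 15% | 99.1 | 98.2 | 97.0 | 92.9 |
| 66 | GS-A, 40% v 20% | 65.1 | 59.9 | 53.7 | 47.4 |
| 66 | GS-S, 60% v 30% | 91.3 | 88.5 | 83.6 | 77.0 |

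An uncorrected chi-square raises GS-A to 63.2% (n=32) and 74.9% (n=42) at zero loss, still short of 80% and 90%.

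**4. Could an allowance already be inside the sizes?** Inflating the uncorrected 27/36/58 by 1/(1−d) gives 31/41/66 at 12% and 32/42/67 at 13%. That is close to 32/42/66, so the numbers alone cannot rule out an unrecorded allowance.

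**The case against.** A reader might infer that the quoted sizes simply fail to deliver the quoted power, and that attrition is the reason. The documents do not support that, on four grounds.

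- **The loss rate and the test are both unstated.** With an uncorrected chi-square, 10% loss breaks none of the three statements; at 20%, 42 is a tenth of a point short and only 66 falls materially below its figure. This stands, and makes the shortfall conditional. It does not reassure much, because a plan that names no test cannot claim that margin, and all three fall short at 30%.
- **The 50% risk is not the plan's.** At 60% v 15%, GS-S keeps its stated power for 32 and 42 at every loss examined. In GS-A the stated power is missed with nobody lost. This stands in full: in GS-A, loss worsens a shortfall whose main source is the mismatch of rates.
- **Some protection exists.** The repeat year-4 visit gives a second chance at an acceptable scan, and 2.2 excludes patients unable to return for visits. Both should reduce loss, but neither recovers a patient who leaves. Admission up to age 85 is not evidence of any particular loss rate.
- **Pooling would help.** Section 2.5 says so, if effects are similar across strata. The quoted figures are nevertheless for separate tests in each stratum.

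The possible hidden allowance of 12–13% also stands as a possibility. If it was used, 2.5 should say so, which needs much the same edit.

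**Conclusion.** The point holds in a conditional form. Section 2.5 attaches power to randomised patients, makes no visible allowance for four years of loss or rejected scans, and gives sizes that are best reproduced with complete data. By that calculation (50% untreated risk, Fisher, two-sided 0.05) there is at most about 1.6 points of slack. Loss of 10% costs about 3 to 6 points from the zero-loss figure, and 20% costs about 8 to 11. Under an uncorrected chi-square the same loss is largely absorbed.

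By stratum, loss does not threaten the 32 and 42 in GS-S up to 30%; the 66 drops below 80% there by Fisher only at 30% (77%). In GS-A, 20% loss takes about 12 to 13 points from power that already starts at 53% and 67%.

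No sum in the plan is shown to be wrong, and no enrolment target is stated, so the finding concerns an undisclosed assumption. All loss rates here are assumptions.

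**What to change.** In 2.5:

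1. Restate 32, 42 and 66 as patients with acceptable baseline and year-4 OCTs.
2. Name the test, the alpha and its sidedness, and the untreated risk used for each size. If an allowance for loss was already included, give it.
3. State power separately for GS-A and GS-S with those numbers randomised, over a range of expected loss such as 10–20%. With Fisher's test, 32 per group would read about 47% to 41% in GS-A and 93% to 91% in GS-S; 42 would read about 62% to 54% and 98% to 97%.

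The 71/84/71% figures should not be inserted as the trial's power: they rest on a 50% risk that describes neither stratum.

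This costs a few sentences and no change in enrolment. The downside is a less favourable stated power, most visibly in GS-A. Only if the sponsor wants 32, 42 or 66 evaluable patients per group would more be randomised: at 20% loss, 32/0.8 = 40, 42/0.8 = 52.5 (53) and 66/0.8 = 82.5 (83).
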